[name]  
[name]  
[contact] / [contact]  
<https://herl.pitt.edu/>  
[[contact]](mailto:[contact])

University of Pittsburgh  
US Department of Veterans Affairs  
*Human Engineering Research Laboratories*

Development and Evaluation of PPAL Bedside Commode for Safe Independent Toileting  
Transfers

STUDY25010091: PPAL Field Trial

PPAL Protocol and Statistical Analysis Plan

10/3/25

**Field In Home Testing.** Once participants are screened for eligibility by the research team, they will be scheduled for a home visit. The Study Research Assistant will visit the home and administer informed consent with the end-user and their caregivers. They will be provided with an orientation to study procedures. At this visit, questions will be answered, the presence of at least one caregiver will be verified, and the home will be screened for the ability to accommodate the PPAL in the intended use space. A home evaluation checklist will be used. The RA will ask and record information about their current toileting habits and recollection of toilet related falls and near falls such as loss of balance while transferring to toilet or commode in the past 6 months. The RA will also observe the participant's transfer methods to their customary toilet or commode to ensure that they are an appropriate candidate for the PPAL. The RA will provide the participant with a log book to track information. They will note the number of times they use the toilet or commode each day. They will note the level of difficulty on a scale that starts at 1 or not at all difficult and goes to 10 for extreme difficulty. They will also note the difficulty they have in transferring to the customary toilet or commode, any toileting related falls or near falls, and toileting mishaps such as not being able to make it to the toilet fast enough. Participants can opt to receive a text message to an online survey using Qualtrics that will ask them to record this information if they prefer. A delivery date for the PPAL will be scheduled a minimum of 3 weeks later to allow time to gather baseline data. On the arranged date of delivery, a moving service will pick up the PPAL and accompanying supplies at the Pitt HERL and deliver it to the participant's home. The RA will help

determine the appropriate placement of the device in the designated area. The RA will observe the participant's transfer to their customary commode and score the transfer per OASIS Section GG Toilet Transfers. The RA will demonstrate the PPAL device use, storage and waste management. At present, the PPAL uses a disposable odor suppressing commode receptacle liner placed into the commode bucket. The absorbent pad within the liner turns waste into gel in a few seconds. The receptacle has a lid, as does the receptacle compartment of the PPAL, both of which can be closed until the caregiver is able to change and dispose of the receptacle liner. The RA will request a return demonstration by the end user and caregiver to ensure understanding of proper device use. If safe transfers and ability to appropriately manage waste cannot be adequately demonstrated after training, the dyad will be disqualified from the trial. Once participants are able to demonstrate safe transfers to and from the PPAL and can demonstrate appropriate waste management, cleaning and storage, the RA will score the transfer to and from the PPAL using the OASIS Section GG Toilet Transfer. Baseline surveys will be administered at this visit via a tablet using Qualtrics. The RA will collect the baseline paper logbook and leave a new one to use for tracking both customary toilet or commode and PPAL use. They will do this by noting the number of times per day they use either, along with other measures including difficulty with transfer, falls or near falls and mishaps. The study team will telephone the participants the day after delivery, 3 days later, and weekly thereafter to identify concerns, answer questions, and identify adverse events such as accidental falls or device malfunction or breakage. The participant and their caregivers will also be provided with a number that they can call for technical support if they experience any problems or issues with the device. The device will remain in the participant's home for 6 weeks. At the end of the 6 week trial, the study team will arrange a final study visit date. At that visit, the moving service will retrieve the PPAL and return it to HERL for cleaning, preventive maintenance and repair or refurbishment as needed. The RA will administer the exit surveys and will observe the participant performing a toilet transfer using the PPAL and their customary commode, scoring both using the OASIS GG score. Outcome measures using Qualtrics will be administered and a semi-structured interview will be conducted to ascertain acceptability and satisfaction with the PPAL.

## Stats Plan

### Field (in home) Trial:

Usability and Performance: The SUS and NASA-TLX scales post-trial will be analyzed descriptively to determine if the real-world use of the device has acceptable usability (SUS

scores > 68) and level of performance (NASA-TLX < 50). In addition, device satisfaction using the QUEST 2.0 (total device subscale score) will be determined.

**Utility:** Graphical methods commonly used for data analysis in single-subject designs will be used to examine changes and trends over time in the personal logged daily number of customary and PPAL toilet transfers. These metrics will also be averaged over the first three weeks (baseline period-no PPAL use) and compared to the same measures averaged over the first 3 weeks and last 3 weeks of PPAL use using a repeated measures ANOVA or non-parametric test equivalent.

**Health Outcomes:** Near falls and separately fall incidence will be determined as a rate of occurrence per week averaged over the baseline period (3 weeks) and compared to the intervention period (6 weeks) using a Wilcoxon signed-rank test (given the small sample size). Similarly, the CATOM and SCI-FCS scores will be compared pre-post PPAL use using the Wilcoxon signed-rank test. A Wilcoxon signed rank test will be used to compare the pre-post OASIS Section GG scores.

Our projected sample size for Aim 2 is based on a comparative usability study design wherein we aim to show that using the PPAL is better than the conventional methods of toileting. Research in the usability community recommends to engage between 8 and 25 participants when statistically significant findings are being sought with 10-12 participants being considered a good baseline range. Factoring in a 20% attrition rate we aim to recruit 16 end-users (and their caregivers) resulting in 12 participant completers. We will interview participants that complete study as well as those who do not complete to gain insight into the characteristics of individuals who may be more likely to adopt or use a PPAL longer term.

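### No SUS or NASA-TLX scoring is planned for dyads that begin home use and stop early, so the usability verdict rests on about 12 completers, with no precision measure named

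*Combined protocol and SAP*

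**What the plan says.** Under Usability and Performance, the Stats Plan says "The SUS and NASA-TLX scales post-trial will be analyzed descriptively to determine if the real-world use of the device has acceptable usability", taking SUS above 68 and NASA-TLX below 50 as acceptable. It does not say whether the mean, the median or each participant's score is compared with the cut-off. It adds "In addition, device satisfaction using the QUEST 2.0 (total device subscale score) will be determined", with no time point and no cut-off.

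Field In Home Testing places the surveys after home use at one visit: "At the end of the 6 week trial, the study team will arrange a final study visit date", and there "The RA will administer the exit surveys" along with outcome measures in Qualtrics. The instruments are not listed by visit. Baseline surveys are given at delivery, but the Stats Plan's usability analysis uses post-trial scores only.

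For dyads that do not finish, the sample-size paragraph plans an interview. During home use, "The study team will telephone the participants the day after delivery, 3 days later, and weekly thereafter to identify concerns" and adverse events; no scale is mentioned for these calls. Participants also keep a daily log of both toilets, including transfer difficulty, falls, near falls and mishaps, and the research assistant scores the PPAL transfer on OASIS Section GG at delivery.

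The sample-size paragraph expects 12 completers from 16 recruited end-users, citing 20% attrition. No early-withdrawal survey, analysis population, missing-data rule or measure of precision is given for the usability verdict.

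**The concern.** The verdict is meant to describe real-world use. A dyad that tries the PPAL at home and gives up because it is hard to use bears directly on that question, yet the plan makes no provision for it to contribute a score. If stopping is related to the device, the completers' average will look better than the average among all who tried it. The plan already treats non-completers as informative, since it interviews them to learn who is likely to adopt the device, but that information does not reach the numerical verdict.

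A second, lesser matter is that about 12 scores are set against fixed cut-offs with no SD or interval named. A mean a few points past a cut-off could lie there by chance, and the report as planned need not show this.

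QUEST has no cut-off, so the concern about a verdict does not extend to it.

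**Working it through.** **The plan's own figure.** 12/(1 − 0.20) = 15 and 16 × 0.80 = 12.8, so 16 recruited and 12 completers agree with 20% attrition to within rounding. Taken literally, 16 to 12 is a loss of 4 (25%); 20% of 16 is 3.2. These are losses from all causes and at any time, so the number *m* of dyads that leave after home use begins lies between 0 and 4.

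**Assumptions (none is in the documents).** The mean is compared with the cut-off. Leavers would average SUS 50 (range 40 to 60) or NASA-TLX 65 (range 60 to 70). The SD is 15 (range 12 to 20).

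**Step 1: completer SUS mean at which the all-starter mean equals 68.** With 12 completers and *m* leavers at *x*, this is 68 + (68 − *x*) × *m*/12.

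| Leavers *m* | *x* = 40 | *x* = 50 | *x* = 60 |
|---|---|---|---|
| 1 | 70.3 | 69.5 | 68.7 |
| 2 | 72.7 | 71.0 | 69.3 |
| 3 | 75.0 | 72.5 | 70.0 |
| 4 | 77.3 | 74.0 | 70.7 |

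**Step 2: worked example, completers at 72.** The all-starter mean is (12 × 72 + *x* × *m*)/(12 + *m*).
- *x* = 50: 914/13 = 70.3, 964/14 = 68.9, 1014/15 = 67.6 and 1064/16 = 66.5 for *m* = 1 to 4. The verdict changes only at 3 or 4 leavers.
- *x* = 60, *m* = 4: (864 + 240)/16 = 69.0. The verdict does not change.
- *x* = 40, the low end of the assumed range: 944/14 = 67.4 at *m* = 2, so it changes from 2 leavers.

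**Step 3: NASA-TLX.** The completer mean giving an all-starter mean of 50 is 50 − (*x* − 50) × *m*/12. For *m* = 2 this is 48.3, 47.5 and 46.7, and for *m* = 4 it is 46.7, 45.0 and 43.3, at *x* = 60, 65 and 70.

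**Step 4: precision with 12 scores.** The 95% half-width is t(0.975, 11 df) × SD/√12 = 2.201 × SD/3.464, which is 7.6, 9.5 and 12.7 points for SD 12, 15 and 20. If the true mean SUS were 65, the chance of an observed mean above 68 is 1 − Φ(3/(SD/√12)) = 19%, 24% and 30% for the same SDs.

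**The case against.** A reader might infer that early leavers are barred from scoring. The documents do not say so. The gap is one of silence: no scoring is planned, but none is forbidden. The device has to be collected from a dyad that stops, and the plan pairs collection with the exit surveys, so a team might well give the surveys then. That is possible, but nothing in the plan provides for it.

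A reader might also infer that the verdict is biased in favour of the device. That does not follow. Losses may come before home use: "A delivery date for the PPAL will be scheduled a minimum of 3 weeks later to allow time to gather baseline data", and after training that does not succeed "the dyad will be disqualified from the trial". Dyads lost in those ways have no home use to score. The participant's usual toilet also remains in use, since the second log is for "tracking both customary toilet or commode and PPAL use", so a dyad that dislikes the PPAL can finish the 6 weeks and score it low. On 20% attrition there are about 3 losses in all, so in the worked example with leavers at 50 nearly all of them would have to follow delivery. Device-related stopping would not be invisible either, because the logs, the calls and the interview would show something of it. All of this stands and limits the size of the concern.

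On precision, a descriptive analysis may ordinarily include an SD and does not rule out an interval, and the plan reserves its tests for other outcomes. This also stands. What remains is that no precision measure is named while a conclusion against a cut-off is still to be drawn.

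**Conclusion.** The point holds as a cheap improvement. Followed as written, the plan yields SUS and NASA-TLX scores from about 12 completers and none from dyads that begin home use and stop. The verdict may be too favourable if those dyads stop because of the device. The effect is small if losses are unrelated to the device or come before home use, and the plan does not say when it expects them. A pass by a few points could reverse only with several low-scoring leavers: 3 or 4 in the example with leavers at 50, 2 or more with leavers at 40, none with leavers at 60. A completer mean of 72 was chosen close to the cut-off for illustration; a mean further above 68 would be harder to reverse.

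The missing precision measure is secondary and does not depend on attrition. It rests on the assumed SD and on the mean being the quantity compared. It might be read as calling for an interval that excludes the cut-off before usability is declared acceptable. The documents give no basis for that: this component is descriptive, and at SD 15 any SUS mean from about 58.5 to 77.5 (68 ± 9.5) has an interval that includes 68, so such a rule would seldom settle the question with 12 people.

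**What to change.** 1. State that SUS, NASA-TLX and QUEST will be administered at withdrawal, with the non-completer interview already planned, to every dyad that began home use.
2. Keep the completers' 6-week scores as the post-trial result and report an all-starter result beside it, with the number of dyads lost before and after home use began.
3. For SUS and NASA-TLX, report the mean, SD, 95% CI and number of participants meeting each cut-off. Do not make the conclusion depend on whether the interval includes the cut-off.

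The cost is a few minutes of questionnaires at an existing contact and a few lines of SAP wording. There are two downsides. Some leavers will decline, so the all-starter result may itself be incomplete. Leavers' scores will also reflect shorter use than the completers' 6 weeks, which is why the two results should stand side by side and not replace one another.

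### The three-window test of the PPAL transfer count includes a baseline that is zero by design, so a significant result mainly shows that the device was used; the first-versus-last comparison is not named

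*Combined protocol and SAP*

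**What the plan says.** The Stats Plan, Field (in home) Trial, Utility paragraph, first sets out graphical single-subject methods for "changes and trends over time in the personal logged daily number of customary and PPAL toilet transfers". It then adds a formal comparison for both counts. The sentence opens: "These metrics will also be averaged over the first three weeks (baseline period-no PPAL use) and compared to the same measures averaged over". It goes on to name the two later windows and the method: "first 3 weeks and last 3 weeks of PPAL use using a repeated measures ANOVA or non-parametric test equivalent". No pairwise contrast or follow-up test is named.

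The Field In Home Testing section fixes the timing. After the first home visit, "A delivery date for the PPAL will be scheduled a minimum of 3 weeks later to allow time to gather baseline data". At delivery the research assistant collects the baseline logbook and is to "leave a new one to use for tracking both customary toilet or commode and PPAL use". The device then stays in the home for 6 weeks, which gives the two 3-week windows of use.

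On sample size, the plan states: "we aim to recruit 16 end-users (and their caregivers) resulting in 12 participant completers".

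**The concern.** There is no PPAL in the home during baseline, so the PPAL count in the first window is 0 for everyone, with no variance. The omnibus null hypothesis for this count is that mean use is equal in all three windows, that is, zero throughout. Any real use makes it false. The test therefore answers a question of little interest (was the device used at all?) and not the one that the two use windows seem meant for (did use hold up, grow or fade?).

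Followed as written, the plan would report a p-value for PPAL transfers under the label of utility. That p-value would often be small even if participants had stopped using the device by the second half, and a reader could take it as evidence of utility over the 6 weeks. The comparison that would inform that judgement is not specified. It would have to be chosen after the data are seen, or left to the graphs and window means.

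**Working it through.** **Inputs from the documents.** 12 completers; a 3-week baseline with no PPAL; two 3-week windows of use (21 days each); repeated measures ANOVA or a non-parametric equivalent. The plan's one sample-size figure reproduces approximately: 12 / (1 − 0.20) = 15 recruits against 16 stated, and 16 × 0.80 = 12.8 completers against 12 stated. The point below uses only n = 12.

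**Inputs not in the documents.** Use rate, spread between people, share of participants who use the device, and alpha. These are assumed, and a range is shown.

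**Fixed examples (no distributional assumption).** Each triple is a participant's PPAL count at baseline, first 3 weeks and last 3 weeks. With tied ranks, the Friedman statistic is Q = (k − 1) Σ(R_j − n(k+1)/2)² / (A − C), where R_j are the rank sums, A is the sum of squared ranks and C = nk(k+1)²/4 = 12 × 3 × 16 / 4 = 144.

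Suppose 4 of 12 participants use the device once and 8 never do:

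- Abandoned, (0,1,0): users' ranks are 1.5, 3, 1.5 and non-users' are 2, 2, 2. Rank sums are 22, 28, 22; squared deviations from 24 sum to 4 + 16 + 4 = 24; A = 96 + 54 = 150. Q = 2 × 24 / 6 = 8.0, p = 0.0183.
- Sustained, (0,1,1): users' ranks are 1, 2.5, 2.5. Rank sums are 20, 26, 26; squared deviations sum to 16 + 4 + 4 = 24; A = 150. Q = 8.0, p = 0.0183.

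The Greenhouse-Geisser ANOVA p-value is also the same for both patterns, 0.0388. For the abandoned pattern, the first-versus-last comparison gives exact signed-rank p = 0.125 and paired t p = 0.0388. For the sustained pattern every first-minus-last difference is 0.

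If all 12 behave alike, (0,4,0), (0,4,4), (0,4,1) and (0,2,4) each give Friedman chi-square 24.0.

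**Simulation.** n = 12, baseline fixed at 0, Poisson counts over 21-day windows, gamma-distributed personal rates with CV 1, each person a user with the stated probability, two-sided alpha 0.05, 2000 runs per cell (standard error at most √(0.25/2000) ≈ 1.1 percentage points). Abandoned means no use in the last 3 weeks. Entries are percent of trials rejecting.

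| Users' mean rate, share of users | Omnibus (GG ANOVA / Friedman), sustained | Omnibus, abandoned | First vs last (signed-rank / paired t), sustained | First vs last, abandoned |
|---|---|---|---|---|
| 1 per day, all | 99.0 / 100 | 98.6 / 100 | 5.0 / 5.4 | 100 / 98.6 |
| 1 per day, 75% | 86.7 / 99.8 | 85.5 / 100 | 3.6 / 3.4 | 97.2 / 85.5 |
| 1 per day, 50% | 46.4 / 89.8 | 46.6 / 97.4 | 1.4 / 2.4 | 55.9 / 46.6 |
| 1 per 3 weeks, all | 68.2 / 91.0 | 73.8 / 98.4 | 2.1 / 3.4 | 61.8 / 73.8 |
| 1 per 3 weeks, 50% | 12.8 / 32.5 | 14.8 / 61.2 | 0.4 / 1.4 | 5.8 / 14.8 |

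Under abandonment the GG ANOVA and paired t columns agree exactly. With the first and third windows both zero, the corrected F is the square of that t. What separates the two approaches is the sustained case, where the omnibus test keeps rejecting and the contrast does not.

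A second simulation, with a fixed number of users, mean use 0.25 to 3 per day, CV 0.5 to 1.0 and no change between the two use windows, agrees. Greenhouse-Geisser rejection was 98% to 100% with 12 of 12 users, 87% to 100% with 9 and 38% to 99% with 6. The first-versus-last paired t-test rejected in 2.3% to 5.8% of trials.

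**The case against.** The best defence is one of reading. The plan openly labels the first window as free of PPAL use, and PPAL logging begins only with the second logbook. A sensible analyst might apply the baseline comparison to customary transfers alone and compare PPAL use across its two windows. Splitting the 6 weeks in half makes sense only if the halves are to be compared, and pairwise follow-up to a three-level test is routine. But the text names both counts and sends both into the same three-window test. Leaving the contrast to custom means that it is not pre-specified.

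The consequence is also modest, and that stands. Graphs and window means would reveal abandonment, exit interviews would add qualitative evidence on longer-term use, no success rule rests on this p-value, and only one of the two utility tests is affected.

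Two further points stand in part. The rejection rates depend on assumed use. With half the participants using the device once per 3 weeks, the omnibus test is far from automatic, and the Friedman rates differ by pattern (32.5% sustained, 61.2% abandoned). They differ in the unhelpful direction, however: abandonment is the more likely to be significant. The replacement contrast is also weak under partial adoption, detecting abandonment in only 5.8% (signed-rank) or 14.8% (paired t) of trials in that cell. That is a reason to rest on an estimate with its interval, not to keep a test of a different hypothesis.

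**Conclusion.** The concern holds, for the PPAL count only. The zero baseline is a fact of the design, not an assumption. With 12 completers and wide adoption, the omnibus test is significant at nearly the same rate whether use is sustained or abandoned (about 99% to 100% at one use per day by all). At 75% users the ANOVA figures are 86.7% and 85.5%. As adoption falls, the test loses power but does not become more informative. These rates rest on assumed Poisson use, CV 1 and alpha 0.05; the fixed examples do not. It should be corrected before analysis, but it does not threaten the trial's other results. The customary-transfer comparison has a real baseline, so its three-window test is meaningful.

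**What to change.** In the Utility paragraph, separate the two counts.

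- **Customary transfers:** keep the three-window comparison.
- **PPAL transfers:** drop the baseline level. Report mean transfers per day in the first and last 3 weeks of use, and make the paired first-minus-last change with its 95% CI the planned comparison, with the CI method named in advance.
- **Limits to state:** power is low under partial adoption. An exact two-sided signed-rank test has minimum p = 2 × (1/2)^m with m non-zero pairs, that is 0.125 for m = 4 and 0.0625 for m = 5, so it cannot reach 0.05 with five or fewer. With 50% users and abandonment, 45% of simulated trials at 1 per day and 95% at one use per 3 weeks had five or fewer.
- **Interpretation:** let the interval and the individual graphs carry it, and say that a non-significant change is not evidence of sustained use. At 1 per day, the paired t-interval had a median half-width of 0.18 per day (all users, sustained), 0.57 (all users, abandoned, true change 1.0) and 0.47 (50% users, abandoned, true change 0.5). Its actual coverage ranged from 85% to 98% over the cells examined, so it should be described as approximate.

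PPAL share of transfers and total transfers are optional additions. The cost is a change of SAP wording and one paired comparison of counts already being logged.

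### The sample size rests on a comparative usability aim, but the Stats Plan states no customary-method comparison for SUS, NASA-TLX or QUEST 2.0

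*Combined protocol and SAP*

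**What the plan says.** The last paragraph of the Stats Plan, Field (in home) Trial, states that the Aim 2 sample size is "based on a comparative usability study design wherein we aim to show that using the PPAL is better than the conventional methods of toileting". It then cites a usability rule of thumb (8 to 25 participants, with 10-12 a good baseline) and arrives at 16 recruited and 12 completers.

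The Usability and Performance paragraph of the same section reads: "The SUS and NASA-TLX scales post-trial will be analyzed descriptively to determine if the real-world use of the device has acceptable usability". The criteria are fixed, with SUS "scores > 68) and level of performance (NASA-TLX < 50". For satisfaction, "device satisfaction using the QUEST 2.0 (total device subscale score) will be determined". No customary-method score, paired difference or test appears for any of the three scales.

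The Utility and Health Outcomes paragraphs do name comparisons. Daily transfer counts in the 3-week baseline are "compared to the same measures averaged over the first 3 weeks and last 3 weeks of PPAL use using a repeated measures ANOVA" or a non-parametric equivalent. Near-fall and fall rates are compared between the 3-week baseline and the 6-week intervention period. CATOM, SCI-FCS and OASIS Section GG are compared pre-post.

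On data collection, Field In Home Testing says of the delivery visit that "Baseline surveys will be administered at this visit via a tablet using Qualtrics", and of the final visit that "The RA will administer the exit surveys". The instruments are not named in either place. The log book records difficulty on a 1-10 scale during the customary-only baseline, and transfer difficulty again once the PPAL is in the home.

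**The concern.** A superiority aim framed as comparative usability needs an estimate of PPAL minus customary on at least one usability measure. A fixed cut-off applied to the PPAL alone cannot supply one: it says whether the device clears a benchmark, not whether it improves on what the person already had.

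Two errors become possible. If the customary method scores as well or better, the trial reports acceptable usability, and a reader who takes the sample-size paragraph at its word may conclude that the PPAL is better. If the customary method scores very badly, a PPAL score just short of the cut-off reads as failure although the person's situation has improved greatly.

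Timing matters too. A rating of the customary method by someone who has not yet used the PPAL can only be obtained before the PPAL is introduced, so this has to be settled before the participant's delivery visit.

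**Working it through.** **1. The plan's own figure.** Inputs from the sample-size paragraph: 12 completers, 20% attrition, 16 recruited.
- 12 / (1 − 0.20) = 15, one below the stated 16.
- Forward, 16 × 0.80 = 12.8, or 12 when rounded down. Going from 16 to exactly 12 is 1 − 12/16 = 25%.

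The stated figure is close enough and does not bear on this point. The 12 comes from a rule of thumb. The documents give no alpha, power, effect size or SD, so there is no power calculation to reproduce.

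**2. Aim against analysis.**

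| Measure | Customary-versus-PPAL or pre-post comparison in the Stats Plan |
|---|---|
| Daily transfer counts | Yes: baseline, first 3 weeks, last 3 weeks |
| Falls; near falls | Yes: weekly rate, baseline against 6 weeks |
| CATOM, SCI-FCS | Yes: pre-post |
| OASIS Section GG | Yes: pre-post |
| SUS | None: post-trial, cut-off 68 |
| NASA-TLX | None: post-trial, cut-off 50 |
| QUEST 2.0 | None: no comparator and no cut-off |
| Logged difficulty, 1-10 | Collected; no analysis named |

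The comparison is missing exactly where the sample-size paragraph places the aim.

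**3. What a cut-off cannot distinguish.** NASA-TLX scores assumed for illustration; lower is better, as the plan's cut-off implies.
- PPAL 45, customary 35: passes (45 < 50); difference 45 − 35 = +10, PPAL worse.
- PPAL 45, customary 70: passes; difference 45 − 70 = −25, PPAL better.
- PPAL 55, customary 80: fails (55 > 50); difference 55 − 80 = −25, PPAL better.

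The first two get the same verdict with opposite comparative answers. The last two have the same improvement with opposite verdicts.

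**4. What a paired comparison in 12 completers would give.** The half-width of a 95% t interval is t(0.975, 11 df) × SD / √12 = 2.201 × SD / 3.464 = 0.635 × SD, where SD is that of the paired difference. The detectable differences assume a two-sided alpha of 0.05, 80% power and normally distributed differences, which requires 0.889 SD.

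| Assumed SD of difference | Half-width | Detectable difference |
|---|---|---|
| 10 | 6.4 | 8.9 |
| 15 | 9.5 | 13.3 |
| 20 | 12.7 | 17.8 |
| 25 | 15.9 | 22.2 |

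Paired t-test power is 35% at 0.5 SD, 71% at 0.8 SD and 88% at 1.0 SD. By simulation (4,000 runs) the Wilcoxon signed-rank test has about 81% power at 0.95 SD.

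Applied to step 3 with an SD of 20, an observed +10 gives −2.7 to 22.7 and an observed −25 gives −37.7 to −12.3. The intervals are wide, but they separate two situations that the cut-off treats as one.

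**The case against.** The strongest reply is that the stated aim is superiority over conventional toileting, not superiority on SUS, NASA-TLX or QUEST 2.0, and that the plan compares six other outcomes within person. That stands. A reader might infer that the trial has no comparison with customary toileting at all; the Utility and Health Outcomes paragraphs show otherwise. What it leaves unanswered is that the sample size is explicitly tied to a usability comparison, and none of the compared outcomes is one that the plan assigns to usability, workload or satisfaction.

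Second, the unnamed baseline surveys might include these scales for the customary method. That also stands: a reader might infer that the scales are never collected for it, and the documents do not support this. They support only that no comparison using such scores is planned. Moreover, those surveys are described after PPAL training and return demonstration, so a customary rating taken then could be coloured by the new device.

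Third, the Usability paragraph asks a narrower question, whether usability is acceptable, and the plan answers it. Nowhere does the plan say that passing a cut-off will be read as superiority. True: the misreading is a risk created by two paragraphs that do not match, not a planned inference.

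Fourth, with 12 completers a paired comparison would often be inconclusive. The power figures above bear this out, and they are why an estimate with an interval is preferable to reliance on a test.

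**Conclusion.** The point holds in a limited form. The Stats Plan justifies its sample size by a comparative usability aim but states no customary-method comparison for SUS, NASA-TLX or QUEST 2.0. As written, superiority can be partly addressed on utility and health outcomes and not on usability.

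This is an inexpensive improvement rather than a defect that undermines the trial. The documents give no basis for saying how likely a misleading verdict is: the NASA-TLX scores in the illustration are assumed, as are the SDs, alpha and normality behind the precision and power figures. The mismatch between aim and analysis depends on none of those assumptions.

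**What to change.** 1. **Analyse what is already logged.** Add to the Usability and Performance paragraph a within-person comparison of the 1-10 transfer difficulty: each participant's baseline mean on the customary method against the mean for PPAL transfers, with the mean or median difference and its interval. State that the second log book uses the same 1-10 scale and records difficulty separately for the PPAL and the customary method; the description of that log confirms neither. No new instrument and no added burden beyond what the log already asks.

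2. **Add a customary-method rating.** Administer NASA-TLX and SUS for the customary toilet or commode at the delivery visit, after the customary transfer is observed and before the PPAL is demonstrated. Report the paired PPAL-minus-customary difference with its interval, and keep the cut-offs as a secondary description. This means splitting the tablet session, which is currently described after training. The cost is a few extra minutes for the participant (assumed; no timings are given) at a visit already planned, and intervals will be wide. QUEST 2.0 can stay descriptive, since its planned score rates a device and the customary method may be an ordinary toilet.

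3. **If neither is adopted, reword.** Remove the comparative-usability rationale from the sample-size paragraph, name which compared outcome carries the superiority claim, and limit the usability conclusion to whether the cut-offs are met. This costs only an edit.

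In any case, name the instruments in the baseline and exit surveys.
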